### **10.8 Defined Safety Evaluation**

A defined safety evaluation will be conducted for the Stage 1 cohort of subjects aged 50 to 64 years, based on the safety data collected through Day 8. The results will be reported to the DMC by treatment group preserving the double-blind status on the subject level, unless the DMC requests unblinded individual treatments. If the DMC concludes that no safety concerns exist, the study will resume enrollment of the remaining subjects aged 50 to 64 years (approximately 736 subjects) as well as all subjects 65 years and older.

### **10.9 Interim Analysis**

There will be a safety and immunogenicity interim analysis based on the data collected through Month 1. The results will be reported by treatment group preserving the double-blind status on the subject level.

For further information, please refer to the VAX31-101 Statistical Analysis Plan (SAP).

## **11. Additional Information**

### **11.1 Ethical Conduct of the Study**

The study will be performed in accordance with the protocol and consistent with ICH GCP Guidelines and applicable local regulatory requirements and laws.

### **11.2 IRB Oversight**

The study (protocol, informed consent form, recruiting materials, and any documents seen by the subject) will be reviewed and approved by an IRB appropriate to each study site. Subjects will

not be recruited, consented, screened, or enrolled until the IRB has approved the required documentation. In addition, the IRB will review amendments to the protocol before their implementation.

The Investigator will retain all correspondence with the IRB in the trial master file and forward copies of all IRB approvals to the Sponsor.

### **11.3 Informed Consent**

The Sponsor or designee will provide a master ICF template to each site for development of a site-specific ICF. At the Investigator's discretion, the site may develop a separate ICF for prescreening as described in Section [6.2](#).

All site-specific ICF must be approved by the Sponsor or designee and the IRB and must be in compliance with ICH GCP, local regulatory requirements, and legal requirements. The Sponsor or designee will advise the site of required changes to the master ICF template during the course of the study.

The Investigator will ensure that each potential study subject is fully informed about the nature and objectives of the study and possible risks associated with participation. Before informed consent is obtained, the Investigator, or a qualified person designated by the Investigator, will provide the potential study subject with ample time and opportunity to inquire about the details of the study, and will answer all relevant questions to the potential study subject's satisfaction. The potential study subject will then decide whether or not to participate in the study. The Investigator, or a qualified person designated by the Investigator, will obtain written informed consent from each study subject before any study-specific activity is performed.

The Investigator will retain the original and any amended signed and dated ICF at the study site and provide a copy to each study subject.

### **11.4 Subject Confidentiality**

The Investigator will ensure that each subject's anonymity is maintained. In all documents submitted to the Sponsor and/or its designee, subjects can be identified by subject ID number and initials. Documents not intended for submission to the Sponsor and/or its designee (e.g., signed ICF) must be maintained by the Investigator securely and must be in compliance with all federal laws and regulations and ICH GCP Guidelines.

## **11.5 Compensation for Injury**

The Sponsor will adhere to local regulations and guidelines regarding clinical study compensation to subjects whose health is adversely affected by taking part in the study. The applicable policy for compensation for injury will be described in the master ICF template.

## **11.6 Clinicaltrials.gov**

For purposes of reporting to clinicaltrials.gov, the Sponsor is the responsible party and will provide information regarding this study in accordance with applicable regulations.

## **11.7 Public Disclosure and Publication Policy**

All publication rights are delineated in the Clinical Study Agreement with the Investigator(s).

## **11.8 Amendments**

The protocol may be amended only by the Sponsor.

The IRB must generally be informed of all amendments prior to implementation. In addition, the Investigator must obtain IRB approval for any amendments likely to affect the safety of study subjects prior to implementation.

The Sponsor may implement an amendment prior to IRB notification or approval only to eliminate an apparent, immediate hazard to study subjects. In that event, the Sponsor will notify the IRB in writing within 7 calendar days after the implementation.

Amendments, including descriptions and rationales, will be documented in this section of the protocol.

## 12. Appendix A: Schedule of Events

Study Event	Screening Visit	Visit 1	Visit 2	Visit 3	Visit 4	Visit 5 to Visit 9	Early Termination
	Screening a (-30 days)	Day 1 a	Day 8 (+3 days)	Day 15 – Phone (+3 days)	Month 1 (±3 days)	Months 2, 3, 4, 5, 6 – Phone (±5 days)	
Informed Consent	X						Refer to Section 7.2 for Procedures
Demographics, Medical History	X	X b					
Concomitant Medications	X	X	X	X	X d	X d	
Physical Exam(s), targeted	X	X b					
Vital Signs	X	X c					
Confirmation of Eligibility	X	X					
Randomization		X					
Study Vaccine Administration		X					
Post-vaccination Observation (at least 30 minutes)		X					
Issue eDiary instructions, Ruler, Thermometer; Conduct Training/Retraining		X					
Review eDiary Data			X				
AE Evaluation (Solicited and/or Unsolicited)		X	X	X	X	X d	
Clinical Labs							
Hematology, Chemistry, Urinalysis		X b			X		
Urine Pregnancy	X b	X b					
Serum for Immunogenicity		X b			X		

- a) Screening and Day 1 Visit are encouraged to be combined; however, subjects may screen for up to 30 days prior to randomizing into the study, and a separate Screening visit may be conducted.
- b) Conduct or collect prior to study vaccination (if indicated by updated medical history or change in health status, as applicable).
- c) Vitals to be taken before and  $\geq 30$  minutes after study vaccine administration.
- d) Only NOCI, MAAE, SAE, and associated concomitant medications collected after Month 1.

1. INTRODUCTION AND OBJECTIVES OF ANALYSIS

1.1. Introduction

This statistical analysis plan (SAP) is designed to outline the methods to be used in the analysis of study data to answer the study objective(s). Analysis sets, data handling rules, statistical methods, and formats for data presentation are provided. The statistical analyses and summary tabulations described in this SAP will provide the basis for the results sections of the CSR for this trial.

Analyses planned for the Data Monitoring Committee (DMC) meeting at the end of Stage 1 were described in the separate document “VAX31-101 DMC Charter v1.0” dated 31-OCT-2023.

1.2. Objectives

The primary objectives are:

- To evaluate the safety and tolerability of a single injection of VAX-31 at 3 dose levels administered to healthy adults aged 50 years and older.
- To compare the safety of VAX-31 to that of Prevnar 20® (PCV20) administered to 4 age groups:
 - Subjects 50 years of age and older (i.e. Overall)
 - Subjects 50 to 59 years of age
 - Subjects 60 years of age and older
 - Subjects 65 years of age and older

The secondary objectives are:

- Safety: To assess laboratory value abnormalities and/or potentially clinically significant laboratory values following the administration of VAX-31 at 3 dose levels compared to control groups receiving PCV20 for subjects 50 years and older.
- Immunogenicity: To assess the induction of antibody responses to the 20 serotypes in common in PCV20 and VAX-31, as well as to the additional 11 non-PCV20 serotypes in VAX-31 for the following subpopulations:
 - Subjects 50 years of age and older (i.e. Overall)
 - Subjects 50 to 59 years of age
 - Subjects 60 years of age and older
 - Subjects 65 years of age and older

The exploratory objective is to further characterize the immune response for each treatment group.

2. STUDY DESIGN

2.1. Introduction

This Phase 1/2 parallel-group, randomized, 2-stage observer-blind study is to be conducted in 3 populations of healthy adults, aged 50 to 59, 60 to 64, and 65 years and older. Subjects will be randomly assigned in a 1:1:1:1 ratio to receive either VAX-31 at 1 of 3 dose levels or a single dose of PCV20, the active comparator.

In Stage 1 of the study, 64 subjects (16 for each VAX-31 dose group and 16 for the comparator group) 50 to 64 years of age will be enrolled initially. If the DMC agrees that the study may continue after reviewing data from Stage 1, approximately 736 additional adults aged 50 to 64 years as well as a minimum of 200 adults aged 65 years and older will be concurrently enrolled in Stage 2. Subjects will have screening procedures (physical examination, vital signs, urine pregnancy test for females of childbearing potential), and if eligible, will be enrolled into the study and receive VAX-31 or PCV20 on Day 1. All subjects will have a urine sample collected as well as blood samples drawn for immunogenicity analysis (OPA and IgG) and safety laboratory analysis at Day 1 (before vaccination) and Month 1 (30 days after vaccination). Solicited Adverse Events (AEs) will be collected for 7 days after vaccination and unsolicited safety information for 30 days after vaccination, with Serious Adverse Events (SAEs), New Onset of Chronic Illnesses (NOCIs), and Medically Attended Adverse Events (MAAEs) collected up to 6 months after vaccination.

A defined safety review of data (solicited and unsolicited AE and SAE) through 7 days after vaccination of the 64 subjects in Stage 1 will be conducted by an independent Data Monitoring Committee (DMC) before proceeding with Stage 2 of the study.

The schedule of assessments is in Appendix A, further details available in the study protocol.

2.2. Sample Size and Power

For subjects enrolled in Stage 1 of the study, comprising 64 subjects 50 to 64 years of age, sample size is not driven by statistical assumptions for formal hypothesis testing but is based on the safety objective for the study. With 16 subjects, events that occur at a frequency of 15% or more will be detected with at least 92% probability and events that occur at a frequency of 10% or more will be detected with 81% probability. Therefore 16 subjects in each treatment group are proposed as the basis for the number of subjects in whom to conduct the first safety assessment.

For subjects enrolled in Stage 2 of the study, comprising approximately 736 subjects aged 50 to 64 years as well as a minimum of 200 subjects aged 65 years and older, sample size is not based on statistical justification. A total of approximately 800 subjects aged 50 to 64 (with a minimum of 200 subjects aged 60 to 64), as well as a minimum of 200 subjects aged 65 years and older, should provide sufficient information to assess safety and immunogenicity in the older age groups. The sample size will also be adequate to plan future studies.

2.3. Randomization Methodology

In Stage 1, a group of 64 subjects are planned to be randomized in a 1:1:1:1 allocation ratio i.e. 16 subjects in each VAX-31 dose level group and 16 in the PCV20 group. There will be no stratification factors.

In Stage 2, a total of 736 subjects, with a minimum of 200 subjects aged 60 to 64, along with a minimum of 200 subjects aged 65 years and older, are planned to be randomized in a 1:1:1:1 allocation ratio. The randomization will be stratified by site.

2.4. Blinding

This is an observer-blind study in which all participants, Investigators, and study personnel involved in the conduct of the study, including data management, are blinded to treatment assignment except for:

- Unblinded independent statisticians who will prepare and have access to the randomization code
- Unblinded data manager (Randomization and Supply Management)
- Unblinded pharmacist or designee at site who will prepare Investigational Product (IP)
- Unblinded Administrator at site who will dispense IP
- Unblinded Sponsor Clinical Supply Manager
- Unblinded Clinical Research Associate/Study Monitor who will monitor pharmacy
- Unblinded Lead Clinical Research Associate and Clinical Trial Assistant who will review the unblinded Clinical Research Associate/Study Monitor's reports and manage IP supply orders and inventory
- Unblinded Sponsor Quality Assurance Consultant(s)

Although unblinded to treatment assignment, none of the above roles will have access to unblinded summaries of immunogenicity or safety data.

The following personnel will have access to unblinded data, including individual treatment assignment and individual immunogenicity data, in order to discharge their roles for data analysis and review during the planned Interim Analysis the end of Stage 1 and the Month 1 Analysis:

- The unblinded statistical programming team, and independent support statistician who will prepare unblinded reports for DMC meetings
- The unblinded data managers who will receive the unblinded data and prepare reconciliation reports and generate unblinded queries
- The DMC members who will review unblinded data reports

- The unblinded programming team and the unblinded statisticians who will prepare the unblinded report for Month 1 Analysis.

The blinded programmers and initial blinded statistician might take these roles upon Sponsor approval following a formal unblinding process. In that case, a new blinded statistician will be designed, but no new blinded programmers will be needed. The newly unblinded programmers and newly unblinded statistician will stop interacting with the Sponsor and the rest of the blinded study team until final database lock (DBL).

- Unblinded Sponsor Reviewer Consultant

Other than the above-mentioned personnel, all other individuals involved in the study conduct, statistical analysis and reporting will remain blinded to individual treatment assignments and individual immunogenicity data until official study unblinding at the end of the study.

Sponsor personnel and limited blinded personnel will become treatment-group unblinded and have access to immunogenicity and safety summaries after the interim database lock (iDBL) for the Month 1 Analysis, as described in Section 2.6.

2.5. Interim Analyses

A defined safety evaluation will be conducted for the Stage 1 cohort of 64 subjects aged 50 to 64 years, based on the safety data collected through Day 8. The results will be reported to the DMC by treatment group preserving the double-blind status on the subject level, unless the DMC requests unblinded individual treatments. If the interim safety analysis supports and DMC concludes that no safety concerns exist, the study will resume enrollment of approximately 936 subjects aged 50 years and older.

For further information including the tables, listings and figures (TLF) to be provided for the DMC review, please refer to the VAX31-101 DMC Charter and associated DMC Mock TLFs document.

2.6. Schedule of Analyses

Statistical analyses described in this SAP will be carried out in two stages:

- Month 1 Analysis:

An interim database lock will occur after all subjects have completed the Month 1 visit and their data up to Month 1 visit have been cleaned. Primary Safety and Immunogenicity endpoints will be prepared by a team of unblinded programmers with the support of an unblinded statistician using the live randomization and kit lists and the unblinded immunogenicity data. The exact scope and list of outputs for the Month 1 Analysis will be decided prior to the iDBL by the Sponsor and documented in a separate document.

The results by treatment group will then be available to Sponsor and other study personnel. All blinded personnel, as indicated in Section 2.4, will remain blinded to individual treatment until final database lock. To that effect, no listing of individual data

will be part of the Month 1 Delivery and the remaining outputs will be reviewed first by the Unblinded Sponsor Reviewer to assess potential unblinding. The Unblinded Sponsor Reviewer will redact any results by treatment group that may be unblinding and provide the redacted outputs to the wider blinded team.

- **Final Analysis:**

The final DBL will occur when all subjects have completed the study, and all data through the last Month 6 visit have been cleaned. Individual Treatment unblinding will be available to all study personnel after the final DBL. The Final Analysis will include all analyses described in this SAP. A single completed CSR will summarize immunogenicity data and safety findings through Month 6 for all subjects.

3. STUDY ENDPOINTS

3.1. Efficacy Variables

No Efficacy endpoint has been defined for this study.

3.2. Safety Variables

Safety assessments performed during the study included solicited AE up to Day 8 and monitoring of unsolicited adverse events, physical examinations, measurement of vital signs, clinical laboratory evaluations including hematology, serum chemistry, and urinalysis. See Section 6.2.5 for the definition of age group.

The primary endpoints are:

- Percentage of subjects reporting solicited local reactions within 7 days after vaccination (redness, swelling, and pain at injection site) in each age group.
- Percentage of subjects reporting solicited systemic events within 7 days after vaccination (fever, headache, fatigue, muscle pain, and joint pain) in each age group.
- Percentage of subjects reporting unsolicited AE within 1 month after vaccination in each age group.
- Percentage of subjects reporting SAEs within 6 months after vaccination.
- Percentage of subjects reporting NOCIs within 6 months after vaccination.
- Percentage of subjects reporting MAAEs within 6 months after vaccination.

The secondary endpoint related to Safety assessments is:

- Safety: Percentage of participants with laboratory value abnormalities and/or potentially clinically significant laboratory values at 1 month after vaccination.
- Safety: Change from baseline in laboratory parameters at 1 month (30 days) after vaccination

3.3. Immunogenicity Variables

Immunogenicity samples will be collected for all subjects at Day 1, Month 1 and at the Early Discontinuation Visit for subjects discontinuing before Month 1 visit. Immunogenicity parameters to be determined include OPA and IgG assays.

The secondary endpoints related to Immunogenicity assessments are:

- 31 VAX-31 Pneumococcal serotype-specific OPA geometric mean titers (GMT) at 1 month after vaccination.

- 31 VAX-31 Pneumococcal serotype-specific IgG geometric mean concentrations (GMC) at 1 month after vaccination.

The exploratory endpoints are all evaluated at 1 month after vaccination:

- GMFR in serotype-specific OPA
- GMFR in serotype-specific IgG
- Percentage of participants with fold rise ≥ 4 in serotype-specific OPA
- Percentage of participants with fold rise ≥ 4 in serotype-specific IgG
- Geometric mean ratio (GMR) of serotype-specific OPA and IgG
- Proportion achieving an OPA titer of at least the serotype-specific LLOQ of the assay
- Reverse cumulative distribution curves for OPA titers and IgG concentrations

4. ANALYSIS SETS

4.1. Analysis Set Definitions

The following Analysis sets will be evaluated and used for presentation and analysis of the data:

- **Screened Population**: Includes all screened subjects who provided informed consent and were assigned a study subject number, regardless of whether the subject was randomized or not. This population will be used to account fully for subject disposition, starting with the informed consent. The screened population will not be analyzed as such but will be available in the clinical database.
- **Randomized Population (RND)**: Includes all subjects from the Screened Population who consented, provided demographic and other Baseline Screening measurements, and were randomized. Each subject will be analyzed as randomized.
- **Exposed Population (EXP)**: Includes all subjects from the Screened Population who received at least one study vaccine administration. Each subject will be analyzed as treated.
- **Safety Population (SAF)**: Includes all subjects in the Exposed Population but excluding subjects lost to follow up at Day 1 reporting no solicited or unsolicited AEs. Each subject will be analyzed as treated.
- **Immunogenicity Evaluable Population (IEP)**: Includes all subjects in the Exposed Population who:
 - Had no major protocol deviation that would impact immunogenicity assessment or other reason to be excluded as defined prior to unblinding or analysis.
 - Had not received a prohibited medication or vaccine. Identification of subjects receiving prohibited medications will be done via a medical review from the Sponsor of a listing of all concomitant medications, and PD will be requested to be added by the Investigator if they were not entered yet.
 - Provided evaluable serum sample results for baseline, the relevant post-vaccination time points, and within the required time frames:
 - Baseline: Day 1 or within 30 days before first study vaccine administration
 - Month 1: Day 25 through Day 35, inclusive

Each subject will be analyzed as treated.

“As randomized” means according to the vaccine regimen to which the subject was randomized, while “as treated” means according to the vaccine regimen a subject received, rather than the vaccine regimen to which the subject may have been randomized.

The RND will be used for the analysis of exposure.

The SAF will be the primary set for the analysis of the safety parameters.

The IEP will be the primary set for the immunogenicity analysis, with the EXP set as supportive.

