## **6.10 Acute Observation**

The subject will be monitored by blinded study staff for signs of an acute adverse reaction for at least 30 minutes after the injection and the blinded study staff will document any AE. Vital signs will also be obtained at least 30 minutes after the injection.

Allergic reactions to the study vaccine are possible; therefore, appropriate drugs and medical equipment to treat acute anaphylactic reactions must be immediately available and a medically qualified study team member trained to recognize and treat anaphylaxis must be present in the clinic during the entire post-dosing monitoring period.

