## **6.19 Early Termination**

An individual subject is considered to undergo Early Termination if the subject stops study participation before the Month 6 visit.

An enrolled subject may voluntarily withdraw consent for further participation at any time before the Month 6 visit. The Investigator will request (but cannot require) such subjects to provide the reason(s) for withdrawal of consent and to undergo an Early Termination visit.

In addition, the Investigator, at his or her discretion, may withdraw a subject from further participation in the study. Criteria for withdrawal by the Investigator include:

- Noncompliance with the protocol
- Pregnancy
- Immediate hypersensitivity reaction associated with a study injection

- Lost to follow-up status requires documentation of at least 3 unsuccessful attempts to contact the subject. Lost to follow-up will be determined after the date of the subject's projected last visit.
- Other reason(s) which, in the opinion of the Investigator, indicate that continued participation in the study is not in the best interest of the subject.

The Investigator or designee must report any early termination for safety reasons to the Sponsor Medical Monitor or designee within 24 hours of discontinuation. Additional information regarding ongoing AE may be provided as a follow-up report.

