### **10.4 Populations for Analysis**

**Randomized Population:** All screened subjects who have informed consent, provide demographic and other baseline measurements, are randomized, and are assigned a study subject

ID (number). Each subject will be analyzed as randomized (i.e., according to the vaccine regimen to which the subject was randomized).

**Exposed Population:** All subjects who receive 1 study vaccination.

**Safety Population:** All subjects in the Exposed Population who provide safety assessment data. This generally includes any subject in the Exposed Population that is not lost to follow-up at Day 1, as they will be at risk for reporting an SAE. Each subject will be analyzed as treated (i.e., according to the vaccine regimen a subject received, rather than the vaccine regimen to which the subject may have been randomized).

**Immunogenicity Evaluable Population:** For this Phase 1/2 study, the immunogenicity population will be analyzed as treated (i.e., according to the vaccine regimen a subject receives, which may be different from the vaccine regimen to which the subject is randomized in the case of treatment errors).

The Immunogenicity Evaluable Population (IEP) includes all subjects in the Exposed Population who:

- Have no major protocol deviation that would impact immunogenicity assessment or other reason to be excluded as defined prior to unblinding or analysis.
- Have not received a prohibited medication or vaccine.
- Provide evaluable serum sample results for baseline, the relevant post-vaccination time points, and within the required time frames:
  - Baseline: Day 1 or within 30 days before study vaccine administration
  - Month 1: 30 days after vaccination  $\pm$ 5 days, inclusive

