6.2.6. Missing, Unused, and Spurious Data

Binary endpoints / Continuous data:

Missing data are assumed to be missing at random and ignorable. Missing data will not be estimated or imputed. Denominators for percentages will be based only on the number of subjects with non-missing values.

The only exception are some derived Day 1 to Day 7 endpoints for solicited AEs. Additional details for handling of missing data in these cases can be found in Section 6.5.1.1.

Dates:

For partial or missing AE start dates the following imputation rules will be applied:

1. If year is not missing and is after the year of first dose:
 - a. If month is missing, then month will be imputed as January.
 - b. If day is missing, then day will be imputed as the first of the month.
2. If year is not missing and is the same as the year of the first dose:
 - a. If month is missing, then impute the month as the month of the first dose date.
 - b. If day is missing, and the month is the same as the month of the first dose date, then impute day as the day of the first dose date.
 - c. If day is missing but month is after the month of first dose date, then impute day as the first day of the month.
3. If year is missing, then impute the year as the year of the first dose date:
 - a. If month is missing, then impute the month as the month of the first dose date.
 - b. If day is missing, then impute the day as the day of the first dose date.
4. If the start date is completely missing, but the AE is either ongoing (i.e. AE stop date is missing) or the stop date is after the first dose date then impute the start date as the first dose date.
5. For any cases involving the rules above, if the AE end date is before the AE start date, then do not impute the AE start date and assume that the AE is treatment emergent/concomitant for the purpose of the analysis. Further, if the AE stop date occurs prior to the first dose date, do not impute the AE start date, and assume that the AE is not treatment emergent.

No imputations will be applied to AE stop dates or other dates. As indicated above, AEs with missing stop date are considered ongoing.

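### SAP Safety Population: a vaccinated subject lost at Day 1 is dropped only if no AE was reported, so membership depends on the outcome (small effect, low severity)

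*SAP*

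**What the plan says.** SAP 4.1 takes the Exposed Population and forms the Safety Population by "excluding subjects lost to follow up at Day 1 reporting no solicited or unsolicited AEs". The same section states: "The SAF will be the primary set for the analysis of the safety parameters". SAP 6.5 produces all safety summaries on this set, including the vital-sign summary in SAP 6.5.3, which compares values before and after vaccination.

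Protocol 10.4 defines the set differently: "All subjects in the Exposed Population who provide safety assessment data". It then explains: "This generally includes any subject in the Exposed Population that is not lost to follow-up at Day 1". Neither sentence refers to whether an AE occurred. SAP 7 declares no change from the analyses defined in the protocol.

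Two further provisions bear on the point. Protocol 6.10 has every vaccinated subject monitored "for at least 30 minutes after the injection and the blinded study staff will document any AE", with vital signs also taken at least 30 minutes after the injection. SAP 6.2.6 states: "Denominators for percentages will be based only on the number of subjects with non-missing values". For the 7-day solicited summaries, SAP 6.5.1.1 treats a subject as missing only when no grade was recorded on any of the seven days.

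**The concern.** The clause makes membership of a safety set depend on the safety outcome. A subject lost at Day 1 who reported an AE enters both numerator and denominator. A subject lost at the same time who reported none leaves the denominator. No missing data need be involved: if Protocol 6.10 was followed, the second subject was observed for 30 minutes, any AE would have been written down, and post-dose vital signs exist. That subject nevertheless leaves the vital-sign summary as well, solely for being AE-free.

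The primary endpoints are AE percentages, and the primary objectives include comparing VAX-31 with PCV20 on them. Relative to all vaccinated subjects, the rule can push the unsolicited AE, SAE, NOCI and MAAE percentages up. If early loss differs between arms, part of the between-arm difference comes from the rule. The AE condition is also a SAP addition that is not listed as a change.

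**Working it through.** **A figure in the plan.** Neither document gives a figure for Day 1 loss or for its effect. The only design calculation is the Stage 1 detection probability with 16 subjects, and it reproduces: 1 − 0.85^16 = 0.9257 (stated as at least 92%) and 1 − 0.90^16 = 0.8147 (stated as 81%). The present point does not depend on it.

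**Inputs.**
- n = 250 per arm (Protocol 10.3).
- n of about 50 per arm aged 65 and older: the minimum of 200 divided by 4. This is approximate, because randomization is not stratified by age.
- Illustrative rates from the VAX-24 groups (Protocol 2.1): unsolicited TEAE 12.3%, MAAE 11.3%, NOCI 1.9%, SAE 1.2%.
- k = vaccinated subjects per arm lost at Day 1 with no AE. The documents do not give it; I assume 0 to 5. Five of 50 would be heavy early loss and is only the top of the assumed range.
- The denominator for unsolicited AE, SAE, NOCI and MAAE is taken to be the number in the Safety Population, since the SAP gives no separate missing-data rule for them.

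**Shift relative to the Exposed Population.** The dropped subjects have no event, so the event count x = p·n is unchanged. The percentage goes from x/n to x/(n − k), and the relative inflation is k/(n − k).

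At p = 12.3%, x = 30.75 for n = 250 and x = 6.15 for n = 50:

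| k dropped | n = 250 | n = 50 |
|---|---|---|
| 0 | 12.30% (0) | 12.30% (0) |
| 1 | 30.75/249 = 12.35% (+0.05) | 6.15/49 = 12.55% (+0.25) |
| 3 | 30.75/247 = 12.45% (+0.15) | 6.15/47 = 13.09% (+0.79) |
| 5 | 30.75/245 = 12.55% (+0.25) | 6.15/45 = 13.67% (+1.37) |

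For the other endpoints with k = 5, the shift at n = 250 is +0.23 points for MAAE, +0.04 for NOCI and +0.02 for SAE. At n = 50 it is +1.26, +0.21 and +0.13.

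**Between-arm difference.** If one arm drops 5 of 250 and another drops none, both at 12.3%, the rule alone creates 0.25 points of difference. With 3 against none it creates 0.15.

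**Scale.** The 95% half-width for one arm at 12.3% is 1.96·√(0.123·0.877/n), which is 4.1 points at n = 250 and 9.1 at n = 50.

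**Solicited endpoints.** A subject lost at Day 1 with no diary entry is already missing under SAP 6.2.6 and 6.5.1.1, whichever safety set is used. The clause matters only for a subject who recorded zeros on Day 1 and was then lost: the diary rule would count that subject as a non-event, and the Safety Population rule removes the subject. At the roughly 70% injection-site pain rate in Protocol 2.1, each such subject adds 175/249 − 0.70 = 0.28 points at n = 250, taking all 250 to have diary data.

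**Against a set that drops every Day 1 loss.** Suppose 5 of 250 are lost and one of them reported an AE. The other 245 contribute 0.123·245 = 30.135 events. Keeping that one subject gives 31.135/246 = 12.66% for an endpoint that counts the AE (+0.36) and 30.135/246 = 12.25% for an endpoint at the same rate that does not (−0.05).

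**What the fix does in the other direction.** If early loss is unrelated to outcome and the lost subjects are counted as event-free, k = 5 gives 0.123·245/250 = 12.05% (−0.25) at n = 250 and 0.123·45/50 = 11.07% (−1.23) at n = 50.

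**The case against.** The best defence is that the SAP is trying to put the protocol's idea into operation. The explanatory sentence in Protocol 10.4 already treats Day 1 loss as the usual reason for leaving the set, and gives as its reason that those followed further remain at risk of reporting an SAE. Someone last seen 30 minutes after injection has not been observed for a 1-month or 6-month endpoint. Keeping such subjects as event-free biases percentages downward by about as much as the clause raises them, and in a safety comparison understatement is arguably the worse error. SAP 6.3.1 also tabulates Exposed and Safety Population counts by treatment and age group and lists set membership by subject, so the number dropped will be visible.

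Most of this stands, and it limits the size and severity of the point. It does not justify the AE condition. Limited follow-up is a reason to treat all Day 1 losses alike, not to sort them by whether they reported an event.

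The defence also rules out several stronger readings that a reader might infer:
- **The SAP set is simply narrower than the protocol's.** It is narrower than the lead definition, but against the explanatory sentence it is broader, because it adds back Day 1 losses with an AE. What can be said is that the texts differ.
- **The rule can only raise percentages.** That holds against the Exposed Population. Against a set without any Day 1 losses, some endpoints move slightly down.
- **All primary endpoints are affected alike.** The diary denominators largely protect the two solicited ones.
- **The set will differ between the Month 1 and final analyses.** Protocol 6.19 says "Lost to follow-up will be determined after the date of the subject's projected last visit", which is Month 6. However, the SAP phrase can also be read as no contact after Day 1, which could be known by the Month 1 lock. A change between locks is possible but not shown.

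**Conclusion.** The point holds as a low-severity error in a stated rule. SAP 4.1 selects the primary safety set partly on AE occurrence, Protocol 10.4 does not, and SAP 7 does not declare the difference. Relative to all vaccinated subjects, the effect at a 12.3% rate is 0.05 to 0.25 points with 250 per arm and 0.25 to 1.37 points with 50 per arm, for 1 to 5 subjects dropped. It is zero if nobody is lost at Day 1 without an AE. These sizes rest on the assumed number of losses, on rates borrowed from VAX-24, and on the Safety Population count being the denominator. They are small beside the sampling error, and SAP 6.2.1 plans hypothesis tests for immunogenicity only, so no planned safety test turns on this. The between-arm comparison is affected only if early loss differs by arm, and nothing in the documents says that it will.

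**What to change.** In SAP 4.1, delete the AE condition and define the Safety Population without reference to AE occurrence: all vaccinated subjects, analysed as treated. If the post-injection check was done for everyone, this is the same as all exposed subjects with any post-vaccination safety observation, the 30-minute check included. Align Protocol 10.4, including its explanatory sentence; if the protocol is not amended, record the difference in SAP 7. Keep the existing non-missing diary denominators for solicited AEs. Add to the disposition table, per arm and age group, the number of vaccinated subjects with no contact after Day 1.

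The cost is about one line in each document and one row in a table. The downside is that the few subjects seen only on Day 1 count as event-free for the 1-month and 6-month endpoints, a possible downward shift of about the size removed. The per-arm count lets a reader judge it.
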